intervention and associated training. This will include salaries, resources, facilities, overheads, and management costs. The cost perspective will be that of the intervention provider, Barnardo's. We will include any costs associated with supervision and additional training and use the time horizon of the trial to estimate staff turnover. We aim to estimate the cost of delivering the intervention in real practice rather than the cost of delivering the intervention in the trial. The cost data will be provided as a mean cost per participant with 95% confidence intervals and be adjusted to occur each year. Data will be collected using activity logs completed by interventionists highlighting all activity associated with a single participating case.

Diversity, equity and inclusion

Participants in research should reflect the diversity of the society where any intervention will be delivered. All the research team will engage in unconscious bias training, training in delivering research to diverse populations. A further part of this work will be to consult both our YPAG and local agencies working directly with the target population to develop not only recruitment and dissemination materials and protocols that promote equitable participation, but to ensure that interventions are themselves suitable for the target populations to be included. This will involve ensuring scenarios and examples used in sessions are culturally inclusive and appropriate. The study has been reviewed by a race equity associate. The study will also undergo an Equality, Diversity and Inclusion Audit (EDIA). A copy of our equality impact assessment is attached as an appendix to this protocol.

Based on our delivery in Bristol to young people being harmed in their communities through substance use, serious violence, and exploitation, we receive referrals showing a disproportionate percentage of racially minoritised young people, we would expect a similar percentage being referred and recruited to the trial.

As was the case during the co-design phase, a group of young people (13-17 to reflect the age groups involved in the study) will be convened monthly. This group (YPAG) will advise on matters pertaining to recruitment (and materials) and the cultural appropriateness of both the intervention and evaluation activities. Involvement will take the form of a monthly group meeting in which specified questions from the wider project team and Equity Team will be brought to the group for discussion. In addition, each session will allow dedicated space for young people to raise any issues identified that may not have been considered already to ensure the avoidance of 'unknown unknowns' (Wynne, 2015) and ground the study within real rather than 'imagined publics'. (Wynne, 2015) Young people that choose to take part in the YPAG will be remunerated £25 (via voucher) for their time, in line with the National Institute of Health and Care Research (NIHR) guidance on public participation in research (NIHR, 2022). The YPAG will be representative of the communities where the research takes place in terms of ethnicity and will purposively sample to ensure diversity for YP with SEN,

LAC and neurodiverse YP. The YPAG will include young people of the target age who have experience of substance use. The YPAG will be managed by a specific member of the research team who has extensive experience in working with YPAG and associated safeguarding issues. Meetings will take place on-line to avoid any potential for iatrogenic effects.

The study has been designed to minimise sources of bias. This includes having enough participants to encompass a diverse population that is representative of the target population, minimising inclusion, and exclusion criteria to reduce barriers to participation, ensuring randomisation is conducted independent of the research team, flexibility in conducting baseline and follow-up assessments to allow those with literacy difficulties to complete assessments verbally if required.

We will actively monitor recruitment on key ethnic, socio-cultural and inclusion parameters and where differences occur in the numbers eligible and the numbers consenting, we will explore the reasons why using qualitative interviews to provide an insight into the cultural and ethnic acceptability of the intervention.

We will conduct qualitative and quantitative analysis to explore the role inequality, ethnicity, and socio-economic disadvantage plays in the outcomes observed.

All materials will be available in both English and Welsh and for those who have difficulties in spoken English or Welsh we will provide a translation service, the need for translations will be assessed at the referral stage. During our co-production phase we identified a high prevalence of potential participants with intellectual disabilities. We will link with existing services to modify the presentation of outcomes to address the needs of the population. This will include using larger fonts, coloured transitions between outcomes, simplification in language used and presenting less text on each page of the outcome assessment. All materials will be considered by our young people advisory panel and should the need for further adaptation be identified during this study, this will be considered by the Equity Team and discussed with the wider project team.

Throughout MDFT's development and testing, racial and cultural issues have been core factors in tailoring interventions to each individual youth and family. Racial and cultural diversity has been one of the hallmarks of MDFT development and in the research supporting the model. In clinical trials of MDFT, 83% of young people and their families were from minority groups. The model has thus developed to address the needs of racial and cultural minority groups, primarily African American and Hispanic families in the Unites States. We recognize that the U.K. 's minority groups will have their own unique historic and cultural issues and themes to address, MDFT has been deemed one of the only empirically established interventions for diverse youth populations in the Unites States. In a review of the research on evidence-based psychosocial treatments, MDFT was ranked the most effective treatment for substance use among African American and Hispanic youth.

Additionally, a meta-analysis examining culturally sensitive substance use treatments indicated that participation in MDFT was associated with significantly greater reductions in substance use. In one MDFT study with youth who were 42% Hispanic, 38% African American, and 11% Haitian or Jamaican, MDFT led to more rapid decreases in drug use than peer group-based cognitive behavioural therapy. In an analysis of data from 5 MDFT clinical trials with a total of 646 adolescents who were 51% African American, 35% Hispanic, and 14% European American, MDFT was more effective than the comparison treatment for every group. The only effective treatment for young African American men in these 5 trials was MDFT.

MDFT research has also identified key processes in successful therapy with minority youth. In MDFT therapy sessions, talking about issues like anger from prejudice, feeling alienated, and the challenges and rites of passage of growing up helped African American youth stay more engaged. Clinically, MDFT delivers culturally sensitive treatment by probing into the multiple systems of the young person's life. We seek the youth's and parents' perspectives on their lives and their interests in popular culture, music, film, social media, and art. Therapists must be aware of how society affects marginalized young people. Positive development is challenging when faced with a clash of cultures, racism, discrimination, prejudice, and with little prospect of meaningful work. MDFT therapists must recognize that adolescents create subcultures with distinct values and norms. In turn, breaking through the strong social control within these groups can be challenging. The shared culture manifests in street language, attire, music tastes, and pastimes. We strive to understand and connect with these young people in their natural environments and during our therapy sessions.

s and registration

The study will be conducted in accordance with the principles of Good Clinical Practice, the Declaration of Helsinki and Caldicott principles. The trial will be registered in an appropriate trial registry. Participants will only be recruited to the study once independent full ethical approval has been granted by the University of Kent Social Research Ethics Committee and Barnardo's. Trial methods and data collection instruments will be assessed by a young person advisory group and their recommendations for changes will be incorporated.

We will ensure participants do not feel coerced to consent. Once a participant is referred to the service any consent to participate in the trial is theirs solely to make. Not consenting to the research will not impact on the BAU they receive, and this will be explained verbally and in writing. If a participant does consent it will be made clear that they can withdraw consent at any time.

We will minimise the potential for participants and staff to experience any adverse or iatrogenic events. In our experience of conducting similar studies in similar populations the risk of adverse events is low, as is the risk of iatrogenic events. We will implement a standard operating procedure for the reporting of adverse events that involves an independent

experienced third-party making recommendations on the severity of any event and whether they are associated with the trial. All staff involved in the study will have enhanced DBS accreditation and will be familiarised with safeguarding practice and procedures.

University of Kent Social Research Ethics Identifier: SRE 1200

Barnardo's Research Ethics Committee Identifier: BREC (23)

Trial Registration: ISRCTN10024151

Data protection

All systems and personnel are approved for the management of clinical and sensitive data and are ISO certified to ISO27001 standard. This includes all physical systems, systems to detect intrusion, encryption of data from point of collection to storage, quality assurance and audit trails associated with any data collected. All identifiable data collected will be done with explicit consent and limited to data to allow participants to be contacted for follow-up. Data linkage will employ a unique identifier where the link to identifiable information will be stored on an encrypted secure database. Researchers will be trained to GCP standard and will comply with all relevant data protection legislation. Once final follow-up is completed, personally identifiable information will be deleted from the dataset held by the university and where consent to the trial has been granted encrypted data will be transferred to the Youth Endowment Fund data archive. Consent for transfer of data will be taken from those resident in England, and data used by DfE, name, DoB and postcode will be transferred. Data collection and management will be governed by a trial specific Standard Operating Procedure agreed and approved by ethics.

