- ERQ13 To conduct a latent class mediation analysis to explore how the volume of violent offences is mediated by the frequency and type of substance used at 6 and 12 months.

Part of this work will be to examine the potential impact of both UK and region-specific issues that may be linked to race, ethnicity, sex, socioeconomic factors and other considerations that may arise which are connected to EDI.

Internal pilot study

Prior to embarking on the efficacy study an internal pilot study will be undertaken. The aim of the internal pilot study is to explore whether it is feasible to deliver MDFT in the UK context and establish key parameters to incorporate into the design of the efficacy study. Progression criteria are detailed in appendix II and the study will be conducted between September 2025 with a transition decision in June 2026.

In the pilot study we will recruit 60 participants, 30 in each arm, across the 2 sites. This will allow for exploration of key parameters needed to confirm sample size calculation for the efficacy study. It is sufficient to allow estimation of two-sided 95% CIs around the proportions of eligible, consenting, adhering and followed up at month 6 in each arm of the study with half-widths less than 0.15. It meets the 30 per group recommended by Lancaster et al (Lancaster et al., 2004) for estimating the SE of a primary outcome with sufficient precision, including accounting for any variation across site, where 12 participants per arm per site is recommended.

Objectives for the internal pilot trial

- **PRQ1** To conduct a prospective, two-arm, individually randomised RCT to pilot study outcomes and methods and establish the parameters for the conduct of efficacy evaluation.
- **PRQ2** To assess whether progression criteria have been met and develop an appropriately powered efficacy protocol.
- **PRQ3** To confirm the pre- post-test correlation on the primary outcome, percent days abstinent from alcohol and/or drugs to incorporate into a sample size calculation.
- **PRQ4** To estimate an estimate of potential effect for the primary outcome for inclusion in a sample size calculation.
- PRQ5 To explore the relationship between the use of alcohol and specific drugs and violent offending. This will be achieved through an analysis of existing datasets; Reframe and RISKIT-CJS, with a confirmatory analysis conducted on the pilot data at the time of transition.

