On completion of assessment battery research staff receive automated message of a referral, randomisation conduct, allocation relayed back to Barnardo's staff who either initiate MDFT or make referral to BAU.

Randomised to BAU (200) Randomised to MDFT (200)

YP referred to alternative service YP allocated MDFT therapist

Outcome assessment at month 6 Outcome assessment at month 6 (n=182) (n=182)

Outcome assessment at month 12 Outcome assessment at month 12 (n=160) (n=160)

Data is collected at 6- and 12-months using bespoke, secure, on-line data collection system and transferred to secure servers managed by the University of Kent. Six- and 12-month data collection is completed by research staff blind to participant allocation and participants receive a payment of £25 for completing assessments at baseline 6- & 12 months.

Sample size calculations

Sample size estimation was conducted in STATA18. A clinically important effect size for substance use frequency in adolescents is estimated as 0.27, similar to the lower bound

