estimates found in systematic reviews of MDFT (Filges T. et al., 2018, van der Pol et al., 2017b). This equates to a number needed to treat of 6, where at least one in six participants receiving MDFT would show clinically important benefits, and a difference in the frequency of substance use of at least 13% in the MDFT group. Detecting an effect size smaller than this provides no additional benefit, the commissioning of services in England and Wales requires the service to achieve a clinically important difference for the target population. To detect this difference, with power at 80% and alpha of 0.05 and a two-tailed test, requires a sample of 480 participants followed-up at the 6-month endpoint. Using data from other studies of substance using adolescents (Coulton S et al., 2023, Deluca et al., 2020) we estimate the prepost-test correlation of the frequency of substance use to be 0.4, and incorporating this into the sample size calculation reduces the number followed-up to 364, 182 in each group. Assuming a loss to follow-up at the endpoint of 10%, similar to other studies in adolescent substance use populations (Coulton et al., 2024) inflates the number needed to randomise to 400. Assuming 80% of those eligible will be willing to consent an indication of acceptability of the study to participants and a lower figure than other studies in similar populations (Coulton et al., 2024) would mean we would need to approach 480 across both sites. Recruitment will be continuous between September 2025 and January 2027, 28 per month will need to be approached in total across both sites per month with the expectation that 24 will consent to participate in the trial across both sites. We anticipate. Based on relative population size that 40% of referrals will come from Newport and 60% from Bristol.

Table 2: Recruitment/ retention table

	Q1	Q2	Q3	Q4	Q5	Q6	Q7	Q8	Q9	Q10	Q11
Months (e.g. Oct-Dec 23):	May-Jul 25	Aug-Oct 25	Nov 25 - Jan 26	Feb - Apr 26	May-Jul 26	Aug-Oct 26	Nov 26 - Jan 27	Feb - Apr 27	May-Jul 27	Aug-Oct 27	Nov 27 - Jan 28
Target number of children and young people referred into the project	0	50	75	75	75	75	75	75	218	360	500
Target number of children and young people recruited to the project and evaluation	0	40	60	60	60	60	60	60	174	288	400
Target number of children and young people who withdraw/drop out	0	4	6	6	6	6	6	6	23	35	40

Table 3: Sample size calculations

		PARAMETER		
Minimum Detectable Effect Size (MDES)		0.27		

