Compliance

We will assess adherence using the MDFT clinical portal, this assesses the dose and duration of interventions planned and delivered including the specific domains targeted at each session. A minimum dose of MDFT is defined as completion of the following metrics over a 6-month period.:

- Adolescent-only Sessions: 55% of total sessions being completed.
- Family Sessions: 30% of total sessions (includes the time within family sessions when therapist might have a little one on one time with youth or parent if needed).
- Parent/ carer-only sessions: 15% of total sessions (maybe with a single parent/ carer alone, and/ or time with the parenting team/ system together.

We plan on conducting a secondary analysis using a Complier Average Causal Effects (CACE) model using an instrumental variable framework. CACE analysis allows us to avoid bias by weighting the ITT treatment effect by compliance with the intervention or control treatment received, this provides an unbiased estimate of the role of compliance in the outcomes observed. By using different thresholds of compliance, a minimum threshold of 12 sessions over 4 months versus complete compliance, we can explore the nature of the relationship between compliance with the intervention and outcomes observed.

Analysis

Pilot study analysis

In the pilot study we will explore the distributional assumptions for each outcome measure and present descriptive statistics, either parametric or non-parametric overall, by allocated group and by stratification variables. We will estimate likely proportions of participants who are eligible, consent and followed up at 6 months. Each of these will be assessed against progression criteria detailed in appendix I (**PRQ1**, **PRQ2**).

We will conduct a descriptive analysis of outcomes including measures of central tendency and estimates of precision for continuous outcomes and proportions for categorical outcomes. Inferential analysis at the pilot stage will focus on the primary outcome and will involve a futility analysis using a fractional regression adjusted for stratification variables. This will allow us to confirm or revise our sample size calculation (**PRQ3, PRQ4**).

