Data from the internal pilot and efficacy study will be combined and analysed blind to group allocation. The efficacy analysis will follow CONSORT guidelines. The primary outcome is fractional, a proportion constrained by 0 or 1. The analysis will be conducted using an analysis by intention to treat and will include all available data to maintain participants as members of their allocated group, irrespective of what intervention was received, this provides an unbiased estimate of effect. To adjust for potential bias from recruiting participants to the pilot or efficacy stage, we will use an individual patient data meta-analysis, entering a dichotomous pilot/efficacy variable into the model as a fixed effect. Differences between the groups will be presented as marginal means and their associated 95% confidence intervals. If the missing primary outcome data exceeds 10% sensitivity analyses will be performed using a pattern mixture approach and multiple imputation to compare the sensitivity of conclusions to varying assumptions about the missing data, particularly whether data is missing at random (MAR) or missing not at random (MNAR) this allows for an assessment of both random and systemic bias.

Secondary outcomes will be assessed in a similar way by establishing diagnostic plots to identify the most appropriate regression approach, including stratification factors and baseline covariates within a multi-level model.

The primary end point is 6 months post-randomisation. This will allow an assessment of impact for short term outcomes. In order to explore whether effects are sustained over time and assess impact on longer term outcomes a secondary analysis will be conducted at 12-months post randomisation.

Exploratory analysis

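### The pilot's observed treatment effect is used to set the sample size, although the protocol fixes the target at 0.27 by clinical importance and pools the same pilot data in the final test

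*Protocol*

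**What the plan says.** Three statements in the protocol combine.

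- **Objectives for the internal pilot trial, PRQ4:** "To estimate an estimate of potential effect for the primary outcome for inclusion in a sample size calculation".
- **Pilot study analysis:** inference on the primary outcome will be a "futility analysis using a fractional regression adjusted for stratification variables. This will allow us to confirm or revise our sample size calculation". The sentence cites PRQ3 (the pre-post correlation) and PRQ4 (the effect).
- **Efficacy study analysis:** "Data from the internal pilot and efficacy study will be combined and analysed blind to group allocation". The only allowance for stage is a pilot/efficacy indicator entered as a fixed effect.

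The section on sample size calculations takes a different view of the target: "A clinically important effect size for substance use frequency in adolescents is estimated as 0.27", and "Detecting an effect size smaller than this provides no additional benefit".

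The pilot has 60 participants, 30 per arm. Its size is justified by the precision of proportions and of the primary outcome's standard error, not by the precision of a treatment effect. The progression criteria in Appendix II contain no effect or futility criterion.

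**The concern.** If 0.27 is the smallest effect worth detecting, the effect seen in the pilot has no role in setting N. A small observed effect is no reason to power the trial for something smaller, and a large one is no reason to power it only for something larger. PRQ4 gives the pilot effect that role.

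The second difficulty is statistical. When N depends on the observed arm difference and the same participants enter an ordinary pooled test, the pilot's weight in the final estimate depends on its own result. If N falls after a favourable pilot, the favourable data are over-weighted. The stage fixed effect absorbs only a difference in mean level between pilot and efficacy participants. A blinded final analysis does not help either, because N has by then been set from an arm comparison. The stated 5% error and 80% power assume a fixed design.

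**Working it through.** **Inputs (protocol).** Effect 0.27; power 80%, two-sided alpha 0.05; correlation 0.4, so variance factor 1 − 0.4² = 0.84; 182 per arm followed up; 10% loss; pilot 30 per arm, hence 30 × 0.9 = 27 per arm analysed. The outcome is treated as approximately normal with unit SD, as a standardised effect implies.

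**1. The plan's own figure.** n per arm = 2 × (1.960 + 0.842)² × 0.84 / 0.27² = 181. The t-based version is 216.3 × 0.84 = 181.7, so 182 per arm and 364 in total. Power at 182 per arm is 0.802. The plan's 364 is reproduced. (The unadjusted 480 is not: 0.27 needs 432 to 434, and 480 × 0.84 = 403. That is a separate matter and does not affect this point.)

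**2. Precision of the pilot effect, 27 per arm.**
- Baseline-adjusted: SE = √(2 × 0.84 / 27) = 0.249, 95% half-width 0.49.
- Unadjusted: SE = √(2 / 27) = 0.272, half-width 0.53. The pilot model lists only stratification variables, so it may lie nearer this value.
- P(estimate ≤ 0 when the truth is 0.27) = Φ(−0.27/0.249) = 0.14, or Φ(−0.27/0.272) = 0.16.
- Power of the pilot itself to detect 0.27: 17 to 19%.

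**3. N if the pilot estimate replaced 0.27** (true effect 0.27, SE 0.249). At the 25th percentile the estimate is 0.102 and N is 1,274 per arm. At the 75th it is 0.438 and N is 69 per arm. At the 10th it is −0.05 and no finite N exists.

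**4. Illustrative operating characteristics.** Two-stage simulation, 2,000,000 replicates per rule: pilot of 27 per arm, N re-solved for 80% power from the pilot estimate and clipped to the bounds shown, and an ordinary pooled test at 1.96. Where there is no stop, an estimate at or below zero sends N to its upper bound. The bounds, this convention and the stop at ≤ 0 are assumptions; the protocol gives none.

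| N per arm | Stop if ≤ 0 | Two-sided type I error | Error favouring MDFT | Power at 0.27 |
|---|---|---|---|---|
| 182 fixed | no | 0.050 | 0.025 | 0.803 |
| 182 fixed | yes | 0.025 | 0.021 | 0.718 |
| 27–182 | no | 0.061 | 0.037 | 0.719 |
| 27–364 | no | 0.064 | 0.039 | 0.835 |
| 27–2,000 | no | 0.065 | 0.043 | 0.849 |
| 91–364 | no | 0.055 | 0.031 | 0.846 |
| 182–364 (upward only) | no | 0.052 | 0.028 | 0.919 |
| 27–364 | yes | 0.038 | 0.033 | 0.702 |
| 91–364 | yes | 0.031 | 0.025 | 0.714 |
| 182–364 (upward only) | yes | 0.027 | 0.022 | 0.787 |

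The power of 0.919 under upward-only revision is bought with a mean N of 259 per arm. The convention for negative estimates matters: re-solving from the absolute estimate with bounds 27–364 gives a type I error of 0.077.

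**The case against.** The strongest reply is that the protocol describes an intention, not a rule, and that every operating characteristic above comes from rules supplied for the check. This stands, and it limits what can be claimed.

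- A reader might infer that the plan inflates type I error. The documents do not establish that. The 6.1 to 6.5% figures need N to be able to fall to pilot size, whereas the timeline plans 340 further recruits. With a floor of 91 per arm the figure is 5.5%, and upward only it is 5.2%. A futility stop alone does not inflate the error: with a stop at zero, the two-sided total falls below 5% under every rule tabulated. The rate favouring MDFT still rises to 3.3% if N may fall to pilot size.
- A reader might infer that power is necessarily lost. Several rules raise it, at the price of a larger trial.
- A reader might infer that the trial will stop on a poor pilot effect. The pilot analysis attaches no stop to the futility analysis, and Appendix II has no effect criterion. The 72% assumes a stop at zero. A stop below −0.1 gives 0.765 and one below −0.25 gives 0.793.
- A reader might call the missing futility boundary an omission. It could be in the statistical analysis plan, which is not shown, so it is not counted here.
- The text says confirm or revise. It does not say that 0.27 is mechanically replaced, so the spread of N in step 3 is the limiting case.

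None of this removes the conflict on the face of the protocol: PRQ4 names the pilot effect as an input to a sample size calculation, and the sample size section makes it irrelevant. A boundary in the analysis plan would not resolve that.

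**Conclusion.** The concern holds in this form: the protocol uses the between-arm effect from about 54 analysed participants to confirm or revise N, contradicts its own clinically fixed target in doing so, and pools those participants with a stage term that does not correct for an effect-dependent N. The firm figures are the pilot's precision (SE 0.25 to 0.27, 95% interval about ±0.5) and the 14 to 16% chance of an estimate at or below zero when the true effect is 0.27. They rest only on the protocol's inputs, 10% loss in the pilot and a normal approximation.

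The consequences for the final test are illustrative. Without a stop, and with negative estimates sending N to its maximum, type I error is about 5.2% (upward only) to 6.1–6.5% (N free to fall to pilot size). Power is 72% rather than 80% if the trial stops at or below zero with N otherwise fixed. Re-estimating the correlation under PRQ3 is ordinary nuisance-parameter revision and is not at fault.

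**What to change.** Change the wording before the June 2026 transition decision.

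1. State in the sample size section that 0.27 remains the target and that the pilot effect estimate will not be used to set N. Delete PRQ4 or make it descriptive only.
2. Limit sample size revision to outcome SD, pre-post correlation and month-6 retention, each pooled over arms and blind to allocation.
3. In the pilot study analysis, remove the futility analysis as a basis for revising N. If a futility look is wanted for its own sake, make it non-binding, state its boundary in advance and report its power cost.

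Restricting revision to increases, or banning every futility look, is not needed to cure the error.

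At the planning values N stays at 364 followed up, with simulated power 0.803 and type I error 0.050. The cost is a text amendment and the loss of an early effect signal at transition, which about 54 participants could not reliably give.
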